**Relationship between Asynchronies and Sleep Disruption in Mechanically Ventilated
Patients: a prospective cohort study.**

NCT05847374

Investigators: [name], [name]

Center: Critical Care Department. Althaia Xarxa Assistencial Universitaria de Manresa.

Address: [name]

Collaborators:

- BetterCare. Sabadell. Spain.
- CerebraHealth. Winnipeg. Canada.

Keywords: Sleep disruption, Patient-ventilator asynchronies, Delirium

First version: December 1, 2018

Current version for *Clinical Trials*: May 5, 2023

INDEX

Abstract	2
Background	3
Study design	3
Study subjects and recruitment	3
Data collection and management	4
Primary and secondary outcomes	4
Statistical plan	4
Trial organization	5
Ethical aspects	5
Funding	5
Experience of the investigator team	5
Strategic Framework and Applicability of the results.....	5
References	6
Appendix 1. CRF of the study	7
Appendix 3. Logbook for confidential identification of enrolled patients	12
Appendix 4. Eligible patients not enrolled in the study	14

Abstract

Mechanically ventilated (MV) patients in the Intensive Care Unit (ICU) are highly susceptible to sleep disruption. Several studies in the last 15 years have demonstrated an extremely poor sleep quality and abnormal sleep pattern evaluated by polysomnography (PSG) devices (the gold standard method for evaluating sleep quality and quantity).

Patient-ventilator interaction is frequently poor leading to asynchronies of varied type and consequences. Moderate-to-severe asynchronies are associated with longer mechanical ventilation, weaning failure and mortality.

The goal of this study is to look for an association between poor sleep quality and patient-ventilator asynchronies.

This study is an observational, physiological study investigating sleep quality and quantity in 50 MV patients by recording modified PSG (Prodigy. CerebraHealth) at night while continuously monitoring 24h/day of patient-ventilator interaction (BetterCare system).

Background:

Sleep is a natural condition that humans need for homeostasis maintenance. Hospitalized patients frequently suffer sleep disruption due to medical conditions and environmental circumstances. Critically ill patients, and specifically mechanically ventilated patients, exhibit severe sleep disruption patterns. Some factors predisposing to sleep disturbances are non-modifiable (age, cerebrovascular disease, but others can be improved (noise, excessive light, sedatives, hypotension). Studies on sleep in ICU patients are scarce due to the cumbersome and technical difficulties of polysomnographic tests. The recent validation of automated sleep studies are a promising field of research.

Delirium is an acute mental disturbance characterized by confused thinking and disrupted attention usually accompanied by disordered speech and hallucinations. Hospitalized, and mostly ICU, patients develop delirium at a variable incidence between 5% and 40% depending on case-mix and individual predisposing factors. Development of delirium during hospitalization is associated with higher mortality and long-term neuropsychological sequela. Because treatment of delirium is very poor, the research agenda is mostly focused in delirium prevention.

The role of mechanical ventilation (MV) on sleep disturbances is not fully understood, but international guidelines recently suggest the use of assist-control modes during sleep. In the MV field, patient-ventilator interaction has gained wide interest after the association of asynchronies with longer MV, weaning failure, and mortality. Nowadays, the availability of systems of continuous monitoring of ventilator waveforms allows the 24-h surveillance of asynchronies in MV patients.

Therefore, our hypothesis is that patient-ventilator asynchronies at night, but also during the day, may be associated with sleep disruption and the secondary development of delirium in critically ill patients.

Study design

This is a prospective observational cohort study involving 50 patients under mechanical ventilation in the Intensive Care Unit.

Study subjects and recruitment

Inclusion criteria:

- Age >18 yr.
- Patients who have survived the initial critical admission phase (severe hypoxemia or shock) and before approaching weaning.
- Consent to participate.

Exclusion Criteria:

- Presence of recent major central nervous system disease impairing consciousness with Glasgow Coma Scale \leq 8T
- Patients with a sleep breathing disorder when it is predominantly central sleep apnea; patients with predominantly obstructive sleep apnea can be included.
- Severe hemodynamic instability (high dose of vasopressors).
- Receiving muscle paralysis.
- Withholding and/or withdrawal of life support treatments.

Patients will retain the possibility to abandon the study at any step without restrictions.

Data collection and management

After enrolment, every night, sleep architecture will be recorded using modified PSG (Prodigy. Cerebra-Health. Canada) (electroencephalography, right and left electrooculography, submental electromyography and electrocardiography) from 24:00 to 8:00. Pulse oximetry (SpO₂) and heart rate will be recorded continuously during the PSG.

Mechanical ventilation will be continuously monitored by Better-Care system with specific algorithms for detection of asynchronies (ineffective efforts during expiration, double-cycling, short cycle, long-cycle, and asynchrony index), with additional capabilities (trapped gas, presence of secretions, pulse pressure variation,...).

Analogo-sedation will be administered as per local protocol. Dosage of continuous analgo-sedation will be recorded hourly by electronic surveillance. Level of sedation will be assessed by Ramsay score, whereas pain will be assessed by Campbell score or Visual Analog Scale when appropriate every 8 hours, or more frequently if deemed appropriate.

Delirium will be assessed by using the Confusion Assessment Method for the Intensive Care Unit (CAM-ICU) every 8 hours (at 08:00, 16:00 and 24:00) from day 0 until discharge.

Sleep protective measures (earplugs, eye mask, avoidance of nocturnal feeding, light and noise reduction) will be routinely administered as per local protocol.

When feasible, sleep studies may be recorded in subsequent days to account for technical losses in the first study, and to get some insights about the trend in sleep disruption during ICU stay.

Outcome Measures

Primary Outcome Measures:

Correlation between sleep architecture (total sleep time, % of rapid eye movement sleep, sleep quantity (or efficiency), slow wave sleep and circadian sleep ratio, % of "pathological/atypical" sleep patterns, and sleep continuity) and asynchronies [Time Frame: 24 hours]

Secondary Outcome Measures:

1. Comparison of sleep disturbances between diurnal and nocturnal asynchronies [Time Frame: 24 hours]
2. Correlation between asynchronies and delirium [Time Frame: Up to 28 days]. Assessed using the Confusion Assessment Method for the Intensive Care Unit each day until ICU discharge.
3. Correlation between sleep disruption and delirium. [Time Frame: Up to 28 days]. Assessed using the Confusion Assessment Method for the Intensive Care Unit each day until ICU discharge.
4. Correlation between heart rate variability, asynchronies and sleep disturbances. [Time Frame: Up to 28 days].

Statistical plan

Sample size:

Based on the exploratory nature of the study, there is no strict sample size calculation, and higher sample size only will reduce the uncertainty of the estimation. Then, we decided a convenience sample of 50 patients.

Analysis:

Continuous variables will be described as mean and standard deviation when normally distributed and by median and interquartile range otherwise. Categorical variables will be described as frequency and percentages.

Continuous variables will be compared by ANOVA test when normally distributed and by Kruskal-Wallis test otherwise. Categorical variables will be compared by chi-square test.

The association of delirium with clinical variables will be analyzed by logistic multivariable regression analysis.

Trial organization

Acceptance by Ethics Committee: December 1, 2018

Actual Study Start Date: January 1, 2019

Actual Primary Completion Date: January 1, 2020

Ethical aspects

The study will follow the legal standards for clinical research in Spain. Specifically, the project needs the approval of the Ethics Committee of the "Unió Catalana d'Hospitals" and informed consent should be obtained from the patient's closest relatives.

The available evidence supports that patients will not be harmed in any way by the participation in this study. Then, no extra insurance coverage is needed.

Funding

This is an investigator-lead study without funding from external sources.

Sleep studies materials will be supplied by CerebraHealth free of charge as a research agreement with Althaia Xarxa Assistencial Universitaria de Manresa.

Asynchronies monitoring is already part of the routine ICU monitoring after an agreement between BetterCare and Althaia Xarxa Assistencial Universitaria de Manresa.

Experience of the investigator team

The investigator team has a wide experience in clinical and physiologic studies in critically ill patients, frequently supported by grants from public agencies.

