Appendix 1. CRF of the study

CASE REPORT FORM (CRF)

Relationship between Asynchronies and Sleep Disruption in Mechanically Ventilated Patients: a prospective cohort study.

CHECKLIST FOR ENROLLMENT

BetterCare software OK: YES NO
 Prodigy available: YES NO
 Informed Consent obtained: YES NO

Study Number: -- --

ICU Admission: Date __ / __ / ____ Hour: __ / __

Age: __ years

Sex: Male Female

Weight: __ __ kg

Height: __ __ cm

COMORBIDITIES: **HEART FAILURE** YES NO
 NEUROMUSCULAR DISEASE YES NO
 COPD YES NO
 DIABETES YES NO
 CANCER YES NO
 RENAL FAILURE YES NO
 LIVER CIRRHOSIS YES NO

ADMISSION DIAGNOSIS: _____

APACHE II ON ADMISSION: __ (sum up the worse values within 24 h of admission)

PUNTAJE	4	3	2	1	0	1	2	3	4
temp.	≥41	39-40.9		38.5-38.9	36-38.4	34-35.9	32-33.9	30-31.9	≤29.9
PAM	≥160	130-159	110-129		70-109		50-69		≤49
frec. card.	≥180	140-179	110-139		70-109		55-69	40-54	≤39
frec. resp.	≥50	35-49		25-34	12-24	10-11	6-9		≤5
Pa/FiO2	<75	76-150	150-200	200-300	>300				
PaO2 (O2<5)					≥70	61-70		55-60	≤55
pH arterial	≥7.7	7.6-7.69		7.5-7.59	7.33-7.49		7.25-7.32	7.15-7.24	≤7.15
sodio	≥180	160-179	155-159	150-154	130-149		120-129	111-119	≤110
potasio	≥7	6-6.9		5.5-5.9	3.5-5.4	3-3.4	2.5-2.9		<2.5
Creat (IRA>2)	≥3.5	2-3.4	1.5-1.9		0.6-1.4		<0.6		
hematocrito	≥60		50-59.9	46-49.9	30-45.9		20-29.9		<20
RB (miles)	≥40		20-39.9	15-19.9	3-14.9		1-2.9		<1
puntaje SNC (puntaje=15-Glasgow)								15 - =	

DAY OF THE STUDY

Data: __ / __ / _____

FiO2: ____	VT: ____ ml	Mode: _____	PEEP: ____	PeakPaw: ____
Resp Rate: ____				
SpO2: _____				
Heart rate: _____				
Systolic blood pressure: _____		Diastolic blood pressure: _____		
Continuous sedatives:	NO []	YES []	Daily dose: _____	
Continuous opioids:	NO []	YES []	Daily dose: _____	
Ramsay:	0-8 h: ____	8-16 h: ____	16-24 h: ____	
Campbell [] VAS []	0-8 h: ____	8-16 h: ____	16-24 h: ____	
CAM-ICU:	0-8 h: ____	8-16 h: ____	16-24 h: ____	

NIGHT SURVEILLANCE

Light reduction:	YES []	NO []	Reason: _____
Noise reduction:	YES []	NO []	Reason: _____
Critical incident:	NO []	YES []	Describe: _____
Extra-sedation:	NO []	YES []	Describe: _____

SOFA Assessment (only during ICU stay)

	Days after enrollment										
	0	1	2	3	4	5	6	7	14	21	28
Respiratory											
Coagulation											
Liver											
Cardiovasc.											
CNS											
Renal											
Total											

Puntuación SOFA					
	0	1	2	3	4
Respiratorio: Po ₂ /FiO ₂	> 400	≤ 400	≤ 300	≤ 200*	≤ 100*

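### Chi-square is the only test named for categorical variables, with no small-count fallback; in the sparsest delirium tables of a 50-patient cohort its uncorrected p-value can be several-fold too small

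*Protocol*

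**What the plan says.** Under Statistical plan, Analysis, the protocol gives one rule for categorical data: "Categorical variables will be compared by chi-square test". It mentions no exact test, small-count rule or continuity correction. The rule just before it, for continuous variables, does have a fallback: ANOVA under normality and Kruskal-Wallis otherwise.

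Under Sample size it says that "there is no strict sample size calculation" and that "we decided a convenience sample of 50 patients". The Background reports delirium at a "variable incidence between 5% and 40% depending on case-mix and individual predisposing factors". Secondary outcomes 2 and 3 relate delirium to asynchronies and to sleep disruption. For clinical variables the protocol adds a model: "The association of delirium with clinical variables will be analyzed by logistic multivariable regression analysis".

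The case report form in Appendix 1 records seven yes/no comorbidities (for example "LIVER CIRRHOSIS YES NO"), and other binary items such as sex, continuous sedatives, continuous opioids, weaning failure and tracheostomy.

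**The concern.** The chi-square p-value rests on a large-sample approximation that is poor when expected counts are small. A cohort of 50 with few delirious patients, split by factors that may be uncommon, produces such tables. The plan foresees a failed assumption for continuous variables but not for categorical ones.

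At stake is the reading of individual results. The protocol treats delirium as its main patient-centred outcome and expects positive findings to be applicable in other ICUs. A link between a comorbidity and delirium could be reported as significant on the strength of one or two patients, where the exact distribution gives much weaker evidence.

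**Working it through.** The 50 is a convenience figure, so there is no calculation of the plan's to reproduce.

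**Inputs.** N = 50 (Sample size). Delirium 5% to 40% (Background), so 50 × 0.05 = 2.5 to 50 × 0.40 = 20 patients. Factor prevalences are not given; a range up to 50% is assumed. No significance level is given; 0.05 two-sided is assumed. Chi-square is taken as uncorrected unless stated.

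**Step 1: expected counts.** With delirium share p and factor share q, both at most 50%, the smallest expected count in the 2×2 table is 50 × p × q.

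| Delirium share | Largest possible value (q = 50%) | q needed to reach 5 |
|---|---|---|
| 5% | 1.25 | impossible |
| 10% | 2.5 | impossible |
| 20% | 5.0 | 50% |
| 30% | 7.5 | 33% |
| 40% | 10.0 | 25% |

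At 10% or less, every such table falls below 5. The same holds for any share under 20%, because 50 × p × 0.5 is then below 5. From 20% upward it depends on q. Giving equal weight to all values of p from 5% to 40%, the share of tables below 5 is 80% if q runs from 5% to 50%, 59% if q runs from 30% to 50%, and 43% if every factor splits 50/50.

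**Step 2: one table by hand.** Take 3 delirious, 3 with the factor, 1 with both. The cells are 1, 2, 2, 45 and the smallest expected count is 3 × 3 / 50 = 0.18.

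- Uncorrected chi-square: 50 × (1×45 − 2×2)² / (3×47×3×47) = 84,050 / 19,881 = 4.23, p = 0.040.
- Fisher: P(no overlap) = (47×46×45)/(50×49×48) = 0.827, so P(one or more) = 0.173.
- Mid-P: P(exactly one) = 3 × 1,081 / 19,600 = 0.165, so p = 0.173 − 0.165/2 = 0.090.
- Continuity-corrected chi-square: 50 × (41 − 25)² / 19,881 = 0.64, p = 0.42.

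**Step 3: other tables at N = 50.**

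| Delirious / factor / both | Chi-square | Corrected | Fisher | Mid-P |
|---|---|---|---|---|
| 3 / 3 / 1 | 0.040 | 0.42 | 0.173 | 0.090 |
| 3 / 10 / 2 | 0.037 | 0.18 | 0.098 | 0.052 |
| 5 / 5 / 2 | 0.018 | 0.116 | 0.072 | 0.038 |
| 4 / 4 / 2 | 0.0012 | 0.023 | 0.028 | 0.014 |

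**Step 4: false-positive rate with both margins fixed** (hypergeometric; delirium 3 to 20, factor 3 to 25). The maximum for uncorrected chi-square is 17.3%, at margins 3 and 3, where any overlap at all counts as significant. The next highest is 11.1%. Over the 324 of 414 margin pairs with an expected count below 5, the mean is 4.4%, and 35% of those pairs exceed 5%. Over the other 90 pairs the mean is 5.2%. With the continuity correction, no pair below 5 exceeds 4.0%.

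**Step 5: false-positive rate with the delirium count random** (binomial; factor groups of 3, 5, 8, 10, 15 and 25).

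| Method | Range |
|---|---|
| Uncorrected chi-square, 5% incidence | 2.0% to 8.6% |
| Uncorrected chi-square, 10% to 40% incidence | 3.2% to 6.1% |
| Continuity-corrected, 5% to 40% | 0.1% to 3.0% |
| Fisher, 5% to 40% | 0.1% to 3.5% |
| Mid-P, 5% to 40% | 0.4% to 5.9% |

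At 5% incidence the six cells, in order of factor group size, are 8.6%, 4.1%, 5.7%, 7.8%, 4.1% and 2.0%. Only groups of 3 and 10 are clearly high.

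**The case against.** The strongest reply is that a small-count rule is ordinary detail for a statistical analysis plan, and one may exist unseen. That carries some weight. But the protocol names a test rather than leaving the choice open, and in the same paragraph gives continuous variables a fallback, so the sentence as it stands can fairly be corrected.

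Several other objections stand and set the limits of the point:

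- The excess needs the uncorrected statistic. The protocol does not say which version is meant, and none of the first three tables in Step 3 is significant after correction.
- A reader might infer that chi-square inflates false positives generally in this study. The figures do not support that: the average is near nominal from 10% incidence upward, and tables with expected counts below 5 have a slightly lower mean (4.4%) than the rest (5.2%). The threshold of 5 is a convention and does not isolate the bad tables.
- A reader might also infer that most delirium tables will be sparse. That depends on factor prevalences the protocol does not state. The 5% to 40% is itself a background range for hospitalised, mostly ICU, patients and not a forecast for this cohort.
- An exact test does not always change the decision. The 5 / 5 / 2 table stays below 0.05 under mid-P (0.038).
- The study is exploratory, its primary outcome correlates mainly continuous measures, and delirium also gets a logistic model. No outcome is defined as a chi-square comparison of delirium by comorbidity.

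**Conclusion.** The concern holds in a narrow form and is minor. The stated rule has no provision for sparse tables. Those are certain for delirium by any binary factor at the low end of the protocol's own incidence range, and possible above it. The damage is to individual p-values in the very sparsest tables, which can be too small by a factor of about four against Fisher (0.173 / 0.040 = 4.3) and about two against mid-P (0.090 / 0.040 = 2.3), and by more in isolated tables such as 4 / 4 / 2. The conditional error rate reaches 17% at one extreme pair of margins.

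This rests on an uncorrected chi-square, a 0.05 two-sided level and delirium near the bottom of the quoted range. Nothing here bears on the primary outcome or on the logistic analysis of delirium.

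**What to change.** Replace the sentence on categorical variables with: *For categorical variables, groups are compared by the chi-square test, or by an exact test (the two-sided mid-P version of Fisher's test) when any expected count is below 5.*

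The change needs no data and keeps chi-square where counts suffice. The cost is some power in sparse tables. It is larger with plain Fisher, whose actual size in the grid is only 0.1% to 3.5%, than with mid-P at 0.4% to 5.9%. Mid-P does not guarantee the nominal level, as its 5.9% upper end shows; anyone who wants that guarantee can name plain Fisher and accept the conservatism.

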Appendix 1. CRF of the study

CASE REPORT FORM (CRF)

Relationship between Asynchronies and Sleep Disruption in Mechanically Ventilated Patients: a prospective cohort study.

CHECKLIST FOR ENROLLMENT

BetterCare software OK: YES NO
 Prodigy available: YES NO
 Informed Consent obtained: YES NO

Study Number: -- --

ICU Admission: Date __ / __ / ____ Hour: __ / __

Age: __ years

Sex: Male Female

Weight: __ __ kg

Height: __ __ cm

COMORBIDITIES: **HEART FAILURE** YES NO
 NEUROMUSCULAR DISEASE YES NO
 COPD YES NO
 DIABETES YES NO
 CANCER YES NO
 RENAL FAILURE YES NO
 LIVER CIRRHOSIS YES NO

ADMISSION DIAGNOSIS: _____

APACHE II ON ADMISSION: __ (sum up the worse values within 24 h of admission)

PUNTAJE	4	3	2	1	0	1	2	3	4
temp.	≥41	39-40.9		38.5-38.9	36-38.4	34-35.9	32-33.9	30-31.9	≤29.9
PAM	≥160	130-159	110-129		70-109		50-69		≤49
frec. card.	≥180	140-179	110-139		70-109		55-69	40-54	≤39
frec. resp.	≥50	35-49		25-34	12-24	10-11	6-9		≤5
Pa/FiO2	<75	76-150	150-200	200-300	>300				
PaO2 (O2<5)					≥70	61-70		55-60	≤55
pH arterial	≥7.7	7.6-7.69		7.5-7.59	7.33-7.49		7.25-7.32	7.15-7.24	≤7.15
sodio	≥180	160-179	155-159	150-154	130-149		120-129	111-119	≤110
potasio	≥7	6-6.9		5.5-5.9	3.5-5.4	3-3.4	2.5-2.9		<2.5
Creat (IRA>2)	≥3.5	2-3.4	1.5-1.9		0.6-1.4		<0.6		
hematocrito	≥60		50-59.9	46-49.9	30-45.9		20-29.9		<20
RB (miles)	≥40		20-39.9	15-19.9	3-14.9		1-2.9		<1
puntaje SNC (puntaje=15-Glasgow)								15 - =	

DAY OF THE STUDY

Data: __ / __ / _____

FiO2: ____	VT: ____ ml	Mode: _____	PEEP: ____	PeakPaw: ____
Resp Rate: ____				
SpO2: _____				
Heart rate: _____				
Systolic blood pressure: _____		Diastolic blood pressure: _____		
Continuous sedatives:	NO []	YES []	Daily dose: _____	
Continuous opioids:	NO []	YES []	Daily dose: _____	
Ramsay:	0-8 h: ____	8-16 h: ____	16-24 h: ____	
Campbell [] VAS []	0-8 h: ____	8-16 h: ____	16-24 h: ____	
CAM-ICU:	0-8 h: ____	8-16 h: ____	16-24 h: ____	

NIGHT SURVEILLANCE

Light reduction:	YES []	NO []	Reason: _____
Noise reduction:	YES []	NO []	Reason: _____
Critical incident:	NO []	YES []	Describe: _____
Extra-sedation:	NO []	YES []	Describe: _____

SOFA Assessment (only during ICU stay)

	Days after enrollment										
	0	1	2	3	4	5	6	7	14	21	28
Respiratory											
Coagulation											
Liver											
Cardiovasc.											
CNS											
Renal											
Total											

Puntuación SOFA					
	0	1	2	3	4
Respiratorio: Po ₂ /FiO ₂	> 400	≤ 400	≤ 300	≤ 200*	≤ 100*
Renal: Creatinina/Diuresis	< 1,2	1,2 - 1,9	2,0 - 3,4	3,5 - 4,9 < 500 ml/día	≥ 5 < 200 ml/día
Hepático: Bilirrubina	< 1,2	1,2 - 1,9	2,0 - 5,9	6,0 - 11,9	≥ 12
Cardiovascular PAM o Fármacos	No hipotensión	PAM < 70	Dopa ≤ 5 ó Dobutamina	Dopa > 5 ó NA ≤ 0,1	Dopa > 15 ó NA > 0.1
Hematológico: Plaquetas	> 150.000	≤ 150.000	≤ 100.000	≤ 50.000	≤ 20.000
Neurológico: GCS	15	13 - 14	10 - 12	6 - 9	< 6

Respiratorio: pO₂/FiO₂ en mmHg. Puntos 3-4 solo se valoran si precisa ventilación mecánica.

Renal: Creatinina en mg/dl. Puntos 3-4 en caso de fracaso renal funcional u oligoanuria.

Hepático: Bilirrubina en mg/dl.

Cardiovascular: PAM (presión arterial media) en mmHg. Fármacos vasoactivos administrados durante más de 1 hora. Dopa = Dopamina. NA = Noradrenalina o Adrenalina (dosis en mcg/kg/min).

Neurológico: GCS = Glasgow Coma Score

OUTCOME:

DELIRIUM: NO

YES

Start: __/__/_____

Hour: __:__

End: __/__/_____

Hour: __:__

WEANING FAILURE: NO

YES

TRACHEOSTOMY: NO

YES

ICU discharge (date): __/__/_____

ALIVE: YES NO

Hospital discharge (date): __/__/_____

ALIVE: YES NO

Appendix 2. Logbook for confidential identification of enrolled patients.

Relationship between Asynchronies and Sleep Disruption in Mechanically Ventilated Patients: a prospective cohort study.

REGISTRY OF ENROLLED PATIENTS (LOGBOOK)

(CONFIDENCIAL AT ENROLLMENT CENTER)

Nº of study patient	Data	Family name/First name	Chart Number	
1	--/ /--			
2	--/ /--			
3	--/ /--			
4	--/ /--			
5	--/ /--			
6	--/ /--			
7	--/ /--			
8	--/ /--			
9	--/ /--			
10	--/ /--			
11	--/ /--			
12	--/ /--			
13	--/ /--			
14	--/ /--			
15	--/ /--			
16	--/ /--			
17	--/ /--			
18	--/ /--			
19	--/ /--			
20	--/ /--			
21	--/ /--			
22	--/ /--			
23	--/ /--			
24	--/ /--			
25	--/ /--			
26	--/ /--			
27	--/ /--			
28	--/ /--			
29	--/ /--			
30	--/ /--			
31	--/ /--			
32	--/ /--			
33	--/ /--			
34	--/ /--			
35	--/ /--			
36	--/ /--			
37	--/ /--			

38	-- / -- / --			
39	-- / -- / --			
40	-- / -- / --			
41	-- / -- / --			
42	-- / -- / --			
43	-- / -- / --			
44	-- / -- / --			
45	-- / -- / --			
46	-- / -- / --			
47	-- / -- / --			
48	-- / -- / --			
49	-- / -- / --			
50	-- / -- / --			

